Intradialytic exercise has been a subject of several investigative studies for the past several decades. A Cochrane systematic review in 2011 found there to be significant benefit in patient's aerobic capacity, resting blood pressure, and health-related quality of life from exercising three times per week for greater than 30 minutes per HD session.⁵ There have been several examples in the literature of exercise studies and subsequent meta-analysis that have shown improvement in many of the physical fitness tests used to measure frailty such as the 6 minute walk test (6MWT), Timed Get up and Go Test (TUG), Maximum Walking Speed Test, Sit to Stand Test (STS) and overall metabolic equivalents achieved.^{6,7,8,9} These exercise routines usually involve either aerobic exercise, resistance exercise or a combination of the two for at least 30 minutes during the 1st two hours of

each HD session. The use of resistance exercises via elastic bands alone has been shown to improve the patient's 30 second STS test and 8-foot TUG test.¹⁰

Despite the known benefits of exercise, there are no formal intradialytic exercise protocols in the United States. The main barriers in the US are thought to be interference with the workflow of an outpatient dialysis center as well as high rates of patient non-adherence and drop out. A German single-center long term study employing exercise professionals measured 1 and 5-year adherence at 78% and 43% respectively.¹¹ Unfortunately the data on adherence and efficacy in the United States is lacking. This remains a challenge across the world as nephrologists and dialysis center staff are thought to lack the personnel and resources needed to advise dialysis patients on individualized exercise regimens.¹²

A test of the feasibility and efficacy of an intradialytic exercise (IDEx) strategy will be the primary intent of this project. This IDEx study will consist of an exercise physiologist consultation with HD patients once a week during their 3 times weekly in-center HD sessions over a 3-month period. At these consultations, exercise physiologists will perform physical assessments and develop individualized resistance exercise plans using elastic bands. The exercise physiologist will continue to visit with the patient once weekly after the initial consultation over the 3-month period. The effects of the resistance exercise regimens on physical function will be measured.

2. Study Aims

The primary objective of this study will be to test the feasibility and efficacy of a 3 month exercise physiologist consultation program. Specifically, our aims will be to:

- a. Test the feasibility of a 3-month exercise physiologist led program
- b. Measure the effect of an exercise physiologist collaboration and intradialytic exercise on the physical function of HD patients using the 30 second STS test,

handgrip strength test [required for frailty scale], 8-foot TUG test and patient physical activity based off of the Low Physical Activity Questionnaire.

3. Administrative Organization

The study will be administered from Satellite Healthcare, Inc., [name]. The study site will be Satellite Healthcare Milpitas. [name].

4. Study Design

a. Experimental design of the study

Randomized controlled trial (RCT) proof of concept study design

b. Study population

Convenience sample from prevalent HD patients from Satellite Milpitas Hemodialysis center in Northern California.

c. Sample size

n=50 (25 intervention - 25 control)

d. Study Outcomes

Feasibility outcomes

- Adherence calculated as the total number of self-reported exercise sessions attempted by the patient when EP not present divided by the total number of hemodialysis sessions. This information will be collected from the patient at the weekly meeting with the EPs.
- Adverse events defined as any injury, impairment or medical condition that was directly or suspected to be due to performing the prescribed exercise.

Efficacy Outcomes

- Change in physical function as measured by the 30 second sit to stand test (STS), handgrip strength test (HGST) and the 8 foot timed up and go test (TUG). Performed prior to initiation of dialysis at their mid-week dialysis session.

5. Study Procedures

a. Subject selection procedures

The Principal Investigator is responsible for screening subjects for the study, ensuring subjects meet all inclusion criteria.

b. Inclusion criteria

- Age 18 years or greater
- Ability to understand and communicate English
- Diagnosis of ESRD and currently undergoing in-center hemodialysis
- On HD for longer than 6 weeks
- Approved by the Satellite Milpitas Medical Director and/or referring physician

c. Exclusion criteria

- Previous major amputations
- Inability to independently ambulate
- Known to be pregnant

d. Recruitment procedures

- The Satellite Healthcare database will be used to identify all in-center hemodialysis patients at the Satellite Milpitas Dialysis Center
- This list of potential subjects will be approved by the Satellite Milpitas Medical Director who will screen to ensure they meet inclusion criteria.
- The study research associate (RA) and PI ([name]) will meet with the potential screened subjects in the dialysis center at the patient's weekly dialysis sessions
- The RA and PI will describe the study using a one-page information sheet and consent form as approved by the IRB.
- The RA and PI will offer the patient to take the information home and discuss with their relatives and significant others
- The RA and PI will then approach eligible participants again to consent to participate in the study. After consent is obtained, participants will be randomized into two groups using sequentially numbered opaque sealed envelopes.

e. Study Intervention

- 12 exercise physiologist consultations over 12 weeks
- Up to 3 exercise physiologists will implement an individualized resistance exercise program using elastic bands

f. Study Measures and Activities

- Subjects will meet with an exercise physiologist once weekly during one of their usual in-center HD sessions over a 3-month period.
- At the initial visit, the following physical function tests will be performed on the patient by EP: STS, HGST and TUG.
- At subsequent consultations, exercise physiologists will provide exercise plans and collect feedback on the exercises from the patients.
- EPs will tailor exercise routines to the individual patients based on a combined aerobic and resistance exercise program.

Aerobic Exercise

Participants will be asked to commence at a minimum of walking 3 times per week commencing at 20 minutes, and increasing both intensity and time up to 30 minutes x 3 times per week.

Resistance Exercise

Participants will be instructed to initially exercise various upper, core and lower body muscle groups using resistance bands for 1 set of 10 repetitions twice weekly. Intensity and repetitions of exercises will be adapted to participants' abilities throughout the 12 weeks. Warm up and warm down exercises will be included where relevant.

- Weekly progress notes and exercise checklists will be employed to monitor the types of exercises used. (see attachments f-h)
- The estimated duration for the appointments will be 30 minutes
- A modified version of the Fried Frailty Index Score will be used to assess for the presence of frailty in both groups at the start of the study. The modification will be the replacement of the Minnesota Leisure Time Activity Questionnaire (MLTAQ) used to measure the low physical activity portion of the FFI with the Low Physical Activity Questionnaire

(LoPAQ). This was previously compared to the MLTAQ in a study of dialysis patients¹⁴.

- Exercise physiologist will encourage patients to complete their individualized exercise routines during their dialysis sessions for which the EP is not present but also at home at their convenience.
- Adverse events can be reported directly to the center manager or the PI. The EP will ask directly about adverse events at every meeting.

6. Data Analysis Plan

Demographic data: age, gender, ethnicity, weight, BMI, end stage kidney disease cause, co-morbid conditions, vintage on dialysis, dialysis treatment details and biochemical indices will be collected. Paired t-test or Wilcoxon-sign-rank will be used to compare the pre and post intervention STS, Hand Grip Test, TUG and modified FFI results depending on the distribution of the data. Patients who drop out or withdraw from the study will be included in the final outcomes with intention-to-treat analysis.

7. Timeline

Timeline (months)	1	2	3	4	5	6	7
Refine protocol							
Staff in-services							
Patient recruitment							
Exercise physiology intervention							
Evaluation interviews							
Data cleaning							
Data analysis							
Papers/Report write up							

IDEx Data Collection Plan

Test	Initial Assessment	Week 1	Week 2	Week 3	Week 4	Week 5	Week 6	Week 7	Week 8	Week 9	Week 10	Week 11	Week 12
Demographic 
 • Name/MR No. • DOB/Age • Gender • Racial Origin • Height • Smoker • Dialysis Vintage (months) • Renal Disease 	x												
Comorbidities 
 • Lung • PVD • Cerebral • Diabetes • Hypertension • Heart Failure 	x												
Dialysis Info 
 • Weight (dry) • BMI • KtV • Hb, PO4, K • Blood Pressure 	x												
Physical Function Tests 
 • Sit to Stand • Timed up and go • Hand Grip 	x											x	
Modified Fried Frailty Index	x											x	
EP Meeting Record	x	x	x	x	x	x	x	x	x	x	x	x	x

References

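### Adherence keeps EP-attended dialysis sessions in its denominator but bars them from its numerator, so full unsupervised exercise during dialysis reads as about 67%, not 100%

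*Combined protocol and SAP*

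**What the plan says.** Section 4d lists adherence first among the feasibility outcomes. It is the "total number of self-reported exercise sessions attempted by the patient when EP not present divided by the total number of hemodialysis sessions". On the source of the data, the section adds: "This information will be collected from the patient at the weekly meeting with the EPs".

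Three places fix when the EP is present. The background describes an "exercise physiologist consultation with HD patients once a week during their 3 times weekly in-center HD sessions over a 3-month period". Section 5e gives "12 exercise physiologist consultations over 12 weeks". Section 5f says: "Subjects will meet with an exercise physiologist once weekly during one of their usual in-center HD sessions". Each EP visit therefore takes place inside a dialysis session that the denominator counts.

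On where exercise may be done, Section 5f encourages patients to follow their routines in dialysis sessions "for which the EP is not present but also at home at their convenience". Resistance work starts "using resistance bands for 1 set of 10 repetitions twice weekly". For walking: "Participants will be asked to commence at a minimum of walking 3 times per week commencing at 20 minutes".

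The progress note (Attachment f) asks at how many of the week's remaining sessions the patient tried the exercises. It asks about aerobic exercise in a separate question. The checklist (Attachment h) has an intake visit, weekly visits 1 to 11 and a visit 12, with a progress note at each of the 12 weekly visits.

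The plan states no total of dialysis sessions, no maximum score and no adherence target.

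**The concern.** A proportion can be read as adherence only if every unit in the denominator could also appear in the numerator. Here the EP-attended sessions are counted below the line and excluded above it. The result is neither the share of unsupervised opportunities taken nor the share of all dialysis sessions with exercise: a patient who exercises at every session, with and without the EP, gets no credit for the EP sessions.

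The definition also leaves open whether exercise at home counts. That decides whether the ratio has a ceiling well below 100% or no ceiling at all.

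Feasibility is Aim a, and the background names non-adherence and drop-out as main barriers in the United States and says that US adherence data are lacking. A figure on an unclear scale would weaken what the study can contribute on that question.

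**Working it through.** There is no stated figure to reproduce; the counts below are derived from the documents.

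**Inputs.** Three dialysis sessions a week, one with the EP (background, Section 5f); 12 consultations over 12 weeks (Section 5e). All scheduled dialysis is assumed to be attended.

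**Sessions.** Total 12 × 3 = 36. EP-attended 12. EP-absent 36 − 12 = 24. The forms give the same count: 12 progress notes × 2 other sessions = 24. That check leaves out the intake visit, which is taken up below.

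**Dialysis-only reading.**

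| EP-absent sessions with exercise | As written (÷ 36) | Matched denominator (÷ 24) |
|---|---|---|
| 24 | 66.7% | 100% |
| 18 | 50.0% | 75.0% |
| 12 | 33.3% | 50.0% |

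**Range of the ceiling.** Section 5e has 12 consultations, while the checklist and the data collection table show 13 contacts (initial plus 12). Three months can also be read as 12 or 13 weeks.

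| Reading | Maximum as written |
|---|---|
| 36 sessions, 13 EP contacts | 23/36 = 63.9% |
| 37 sessions (12 weeks, both end visits counted), 13 contacts | 24/37 = 64.9% |
| 36 sessions, 12 contacts | 24/36 = 66.7% |
| 39 sessions, 13 contacts | 26/39 = 66.7% |
| 39 sessions, 12 contacts | 27/39 = 69.2% |

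**If home sessions count.** Two dialysis sessions plus one home session a week gives 12 × 3 = 36, and 36/36 = 100%. Two plus two gives 48/36 = 133.3%. These home frequencies are illustrative; the point is that the bound disappears.

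**Missing notes (illustrative: 3 of 12 EP visits missed, patient exercises at every EP-absent session).** Recorded attempts are 9 × 2 = 18, or 18 + 3 = 21 if the next note picks up the session that the EP did not attend.
- As written: 18/36 = 50.0% to 21/36 = 58.3%.
- Only sessions covered by a note: 18/18 or 21/21 = 100%.
- All EP-absent sessions, 36 − 9 = 27, unreported counted as not attempted: 18/27 = 66.7% to 21/27 = 77.8%.

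**Drop-out (illustrative: all 8 EP-absent sessions attempted in weeks 1 to 4, then the patient leaves).**
- As written: 8/36 = 22.2%.
- Planned EP-absent sessions: 8/24 = 33.3%.
- Only weeks with a note: 8/8 = 100%.

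A denominator limited to reported weeks thus removes the mismatch but hides non-reporting and drop-out.

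**The case against.** The best defence is that this is a matter of wording. No stated figure is wrong, no threshold, test or go/no-go rule uses the value, and adherence is not compared between arms. Unsupervised attempts per dialysis session can be interpreted if labelled as such, and nothing says that 100% must be attainable. With planned attendance, the matched value is simply 1.5 times the written one.

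Much of that stands, and it limits the consequence to reporting and interpretation. But the factor of 1.5 holds only when exactly one session in three is EP-attended for every patient, and missed visits break it. The plan also calls the ratio adherence, which readers will take as a share out of 100%.

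Three stronger readings are tempting and not supported:

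- **That reported adherence will reach 133% to 167%.** Counting the starting prescription of three walks and two resistance sessions a week gives 12 × 5 = 60 and 60/36 = 166.7%. This adds walks to a numerator that the form keeps apart, and no form question counts home resistance sessions. What can be said is that Section 4d does not exclude them.
- **That the EP visit is itself one of the two weekly resistance sessions, so that fewer unsupervised sessions are prescribed.** The plan does not say so. Section 5f describes the visits as giving plans and collecting feedback.
- **That the ceiling makes the study fall short of the 78% one-year adherence cited in the background.** The documents do not say how that study defined adherence, so the two figures cannot be compared.

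**Conclusion.** The mismatch is real, and no other section repairs it. On the dialysis-only reading the score cannot exceed 66.7%, or 63.9% to 69.2% across the visit counts and durations that the documents allow. At planned attendance it understates unsupervised adherence by a third: 50% is reported where 75% of opportunities were taken. If home exercise counts, there is no upper bound.

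The 66.7% is conditional. It assumes that only exercise during dialysis counts, which the progress note favours but does not settle, and that no dialysis session is missed. A reader might infer that the feasibility conclusion itself is invalid; the documents do not support that, because no conclusion is tied to a value of this ratio. It is a defect in an outcome definition that should be corrected before the figure is calculated.

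**What to change.** Define intradialytic adherence as EP-absent dialysis sessions with exercise attempted, divided by all EP-absent dialysis sessions in the 12-week period, for every patient in the intervention arm, including those who drop out. Then:

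- In the main figure, count sessions with no report as not attempted. Do not restrict the denominator to weeks with a completed progress note; that would sit badly with the intention-to-treat statement in Section 6. Report the number of weeks without a note, and give the covered-weeks ratio only as a sensitivity figure.
- State how sessions after drop-out are classed. The 8/24 above uses the planned two a week. If every later session counted as EP-absent, the denominator would be 8 + 8 × 3 = 32 and the score 8/32 = 25.0%.
- State that home resistance sessions and walks are outside the ratio, and report them separately.
- Reconcile the 12 consultations in Section 5e with the 13 contacts in the checklist and data collection table.

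The cost is small. EP-attended sessions can be counted from the EP Meeting Record. Total sessions must come from treatment records: Section 6 plans to collect dialysis treatment details, which may cover them, but the data collection table does not list sessions attended. One question on home resistance sessions would be added to the weekly note. The downside is a conservative figure when notes are missing, as the 66.7% to 77.8% in the missing-notes example shows for a patient who exercised at every opportunity.

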_____ minutes
10. In the past 7 days, how many hours were you in bed at night? _____ hours/night (average)

11. Do you work outside the home? no yes
if yes, does your job require you to do walking?
 no yes
if yes, your job require you to do physical exertion such as lifting?

(Johanson et al, Characterization of Physical Activity and sitting time among patients on Hemodialysis using a new physical activity instrument. Journal of Renal Nutrition 25:1, 2015 25-30)

f. EP Weekly Progress Note

How did the exercises go in the last week? At how many of your other sessions last week did you attempt to complete your exercises? How many of your aerobic exercises did you complete last week?

Have there been any noticeable changes that you have observed from our last meeting?

Is there anything that you are able to do now that you could not do before (endurance, strength, or flexibility)?

Have you experienced any symptoms or side effects from your exercise? If yes, what were they? (e.g., pain during any of the exercises? Any dizziness or light-headedness during or post-exercise?)

How can we modify the exercises from our last meeting?

Frequency	Intensity	Type	Time
-----------	-----------	------	------

What new exercises should we add or change for this upcoming week? (Document additional exercises for the new week and changes in prescription)

What are your exercise goals for the next week?

g. EP Exercise Plan

WARM UP						
ACTIVITY	SETS	REPS	TIME	DIST	INTENSITY**	NOTES

Aerobic Exercises		
Number of Attempts	Average Time	Average Distance

CORE BODY – STRENGTH TRAINING					
EXERCISES	SETS	REPS	WEIGHT/BANDS	REST TIME	NOTES

UPPER BODY – STRENGTH TRAINING					
EXERCISES	SETS	REPS	WEIGHT/BANDS	REST TIME	NOTES

LOWER BODY – STRENGTH TRAINING					
EXERCISES	SETS	REPS	WEIGHT/BANDS	REST TIME	NOTES

h. EP Weekly Checklist

INDEX VISIT CHECKLIST

1. Initial Intake visit

- Complete the PRE-Study Assessment form for both control and intervention patients.
- Provide intervention patient with an initial Exercise Plan form.
- Make a copy of the Exercise Plan form. Provide one to the patient and place one in the Patient Information binder.
- Scan the PRE-Assessment forms for all patients and email to [name] at [contact]

2. Weekly visit #1-11

- Complete the Progress Note form.
- If any alterations are made to the exercise plan, complete a new Exercise Plan form.

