- Make a copy of the updated Exercise Plan form. Provide one to the patient and place one in the Patient Information binder.

3. Weekly visit #12

- Complete the POST-Study Assessment form for both control and intervention patients.
- Complete the Progress Note form.
- Scan the POST-Study Assessment form for all patients and email to [name] at [contact]

4. Reminders

- Report any adverse events (side effects from exercise) to the Center Manager and email [name] at [contact]
- At any point, a patient may choose to leave the study. If this happens, notify the Center Manager [name] and email to [name] at [contact]

Pre and Post Intervention Assessment

Hand Grip Strength Measurements: Using the Handgrip strength dynamometer take the best of three measurements for the non-fistula arm. If both arms have fistulas, use the arm that is not currently being accessed. If no fistula is present, use the non-dominant arm. Chart whether the left or right arm is used for the test. For the post-assessment make sure it is the same hand used in the pre-assessment. Pause 10-20 seconds between each test.

Handgrip Strength		
Test 1:	Test 2:	Test 3:
Average:		Hand Used:

Timed Up and GO (TUG): Record time in seconds for the patient to walk 8 feet in a straight line and return to a seated position. Patient is allowed one practice run. Two are counted. Note the average of the two. Chart if an assistance device such as a walker or cane is needed and note the type of assistance device.

Timed Up and Go (TUG) (seconds)	
Trial #1:	Trial #2:
Average:	Assistance Device:

Sit-to-Stand: Have the patient sit with arms crossed over the chest stand up and sit down as quickly as possible. Record the number of times they can go from sitting to standing in 30 seconds.

Sit-to-Stand (Repetitions/ Time)	
# of repetitions:	Repetitions/Time:

Low Physical Activity Questionnaire: Administer the questionnaire on the following page as instructed. Scan and email back results of this and the above physical function tests to [contact]. [see attachment e]

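### Adverse events count only if suspected to come from the prescribed exercise, so the control count is zero by construction and the arms cannot be compared; add all-cause events recorded alike in both arms

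*Combined protocol and SAP*

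**What the plan says.** The design is given in section 4a as "Randomized controlled trial (RCT) proof of concept study design", with 25 patients per arm (section 4c). Section 4d lists two feasibility outcomes, adherence and adverse events. The second counts an injury or other medical problem only if it was "directly or suspected to be due to performing the prescribed exercise".

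The collection tools use the same wording:

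- **Section 5f:** "The EP will ask directly about adverse events at every meeting". There is also a spontaneous route: "Adverse events can be reported directly to the center manager or the PI".
- **Attachment f (weekly progress note):** "Have you experienced any symptoms or side effects from your exercise", with pain, dizziness and light-headedness as prompts.
- **Attachment h (weekly checklist, reminders):** "Report any adverse events (side effects from exercise) to the Center Manager".

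The checklist in attachment h gives the initial exercise plan to intervention patients. It names control patients only for the pre-study assessment at intake and the post-study assessment at visit 12. The pre/post assessment form, as printed, has items for grip, timed up and go, sit-to-stand and the activity questionnaire, but none for adverse events. The data collection table has no adverse event row; the nearest is the row for the exercise physiologist's meeting record. Section 6 plans paired pre/post tests of function and frailty and describes no adverse event analysis.

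**The concern.** An event has to pass a causal test before it is counted, and the test refers to something that only one arm is meant to receive. A control patient who falls or is admitted contributes nothing. An intervention patient with the same event contributes only if someone suspects the exercise. The randomised control group therefore gives no background rate for this outcome.

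The error can run in either direction. Harm that is not recognised as related is lost from both arms. Background events that happen to be suspected are set against a control figure that could not have been anything but zero. Adverse events are one of only two feasibility outcomes, and feasibility is half of the primary objective. A report stating some events against none, or none against none, would invite a comparison that the data cannot support.

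**Working it through.** The plan gives no adverse event rate, alpha or power, so there is no figure to reproduce. The main check is a reading of the text. The arithmetic below only sizes the consequences.

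**Inputs from the documents.** 25 per arm (4c); the causal definition (4d); asking at every meeting (5f); intake plus weekly visits 1 to 12 (attachment h and the data collection table); controls named only at intake and visit 12 (attachment h).

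**Assumptions.** Background rates of 10% to 50% over 12 weeks, a fraction f of background events suspected to be exercise-related, two-sided alpha of 0.05, and complete follow-up of all 25 per arm.

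**1. Control count.** Expected qualifying control events = 25 × P(event) × P(suspected due to prescribed exercise | no prescribed exercise) = 25 × P(event) × 0 = 0, for any P(event). The zero comes from the definition and does not estimate risk. An exact upper limit for 0/25 (1 − 0.05^(1/25) = 11.3% one-sided 95%; 1 − 0.025^(1/25) = 13.7% two-sided 95%) would say nothing about control risk. Those limits reflect n = 25, not the size of this problem.

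**2. Asking.** Intervention: 1 intake + 12 weekly = 13 contacts. Control: 1 intake + 1 at week 12 = 2. Over 25 patients that is up to 325 against 50. Leaving out intake, when exercise has not begun, it is 12 against 1 per patient.

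**3. What a naive comparison would do.** The plan does not schedule this test; it shows how a reader could be misled. By Fisher's exact test, 5 vs 0 gives p = 0.0502 and 6 vs 0 gives p = 0.022, so six events would look significant. Suppose exercise does no harm and half of background events are suspected (f = 0.5). Expected intervention patients with an event = 25 × rate × 0.5:

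| Assumed background rate | Expected, intervention | Expected, control | Chance of Fisher p ≤ 0.05 |
|---|---|---|---|
| 10% | 1.25 | 0 | 0.001 |
| 20% | 2.5 | 0 | 0.03 |
| 30% | 3.75 | 0 | 0.16 |
| 50% | 6.25 | 0 | 0.62 |

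With f = 0.25 the last column runs from below 0.001 to 0.08; with f = 1 it runs from 0.03 to above 0.99. The spurious signal is negligible at low rates and serious only at high ones.

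**4. What all-cause recording in both arms would give.** Half-width of the 95% CI for the risk difference at equal rates p = 1.96 × √(2p(1 − p)/25):

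| p | Half-width (points) | Power for a +20-point excess: normal approximation / Fisher |
|---|---|---|
| 10% | 17 | 0.42 / 0.31 |
| 20% | 22 | 0.34 / 0.23 |
| 30% | 25 | 0.30 / 0.23 |
| 50% | 28 | 0.30 / 0.23 |

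For 80% power against a +20-point excess, 62 to 93 patients per arm would be needed.

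**The case against.** The best defence is that the plan never claims to compare safety between arms. Adverse events sit under feasibility beside adherence, which also has meaning only in the intervention arm. The trial is labelled proof of concept, and an exercise-attributed count is a usual tolerability measure. The threshold is also low, since suspicion is enough. All of this stands, and it is why the attributed count should be kept. It does not remove the gap: no background count is collected, and nothing warns against reading the control zero as a result.

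The control condition is also not described. Section 5f says that subjects meet the exercise physiologist weekly without naming an arm, so the intervention-only reading rests on attachment h. If controls were seen weekly, the inequality in asking would shrink, but the causal definition would still exclude their events. Spontaneous reporting is open to both arms, but the same definition applies to it.

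Three stronger readings are tempting and are not supported:

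- **That the staff delivering the programme decide causality.** No section says who adjudicates. Events may go to the centre manager or the investigator, and the exercise physiologists' reports go to the centre manager.
- **That an event not linked to exercise can never surface.** The progress note also asks about noticeable changes since the last meeting, which could bring an event to light and lead to suspicion. That helps only patients who have progress notes.
- **That all-cause recording would be unbiased.** The arms know their allocation, and intervention patients will have been asked about symptoms weekly. Recall of home falls at week 12 may therefore differ between arms.

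**Conclusion.** The point holds as a limit on what the adverse event outcome can show. Under section 4d as applied in attachments f and h, the control count is structurally zero, active asking is up to 13 contacts against 2, and events not suspected to be exercise-related are counted in neither arm. The attributed count describes tolerability in the intervention arm and nothing more. This rests on controls having no prescribed exercise, which the checklist supports but no section states outright.

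A reader might infer that the definition alone stops the trial from showing whether the programme causes harm, and that changing it would let the trial do so. Neither follows. Physical function is measured in both arms, so worsening there could still be seen. With 25 per arm, even all-cause recording would have power of only about 0.23 to 0.42 for a 20-point excess at the assumed rates. The gain is an interpretable, wide estimate in place of a comparison with no meaning. This is a cheap improvement, not a flaw that undermines the trial.

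**What to change.** In section 4d, add a second safety measure: all falls, injuries, hospital admissions and deaths from randomisation to the week-12 assessment, whatever the attribution. Make the following changes with it:

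- **Ascertainment:** the same in both arms. Use the centre's records as the main source, which also covers dropouts for as long as they are treated there. Add one identical question block to the post-study form that both arms already complete.
- **Analysis (section 6):** counts by arm and the risk difference with a 95% CI, labelled descriptive.
- **Attributed events:** keep them as a separate subset for the intervention arm. State that zero attributed events in controls follows from the definition.
- **Control condition:** say in section 5 what controls receive and how often they meet the exercise physiologist.

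I would leave dialysis-session complications out. The term would need a definition, and at three sessions a week for 12 weeks it means 3 × 12 = 36 session records per patient, or 36 × 50 = 1,800 in all.

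**Cost:** one chart review for each of 50 patients at a single centre and one block on an existing form. The downsides are that most recorded events will be unrelated to exercise, that self-reported home falls may be recalled differently by arm, and that the intervals will be wide. The result must not be presented as a safety test.
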